10.1.2.2 Procedures for Recording Adverse Events

Physicians should use correct medical terminology/concepts when recording AEs in the AE section of the eCRF. Colloquialisms and abbreviations should be avoided.

Only one AE term should be recorded in the event field of the eCRF.

See Appendix 3 for further specific instruction regarding:

- Infusion-Related Reactions
- Diagnosis versus signs and symptoms

- Adverse Events occurring secondary to other Adverse Events
- Persistent or recurrent Adverse Events
- Abnormal Laboratory Values
- Abnormal Vital Sign Values
- Abnormal Liver Function Tests
- Deaths
 - All events with an outcome or consequence of death should be classified as serious adverse events (SAEs) and reported to Roche immediately. In certain circumstances, however, suspected adverse reactions with fatal outcome may not be subject to expedited reporting. All deaths that occur during the protocol-specified AE reporting period, regardless of relationship to study medicine, must be recorded in the AE section of the eCRF and immediately reported to Roche
- Pre-existing Medical Conditions
- Lack of Therapeutic Efficacy
- Hospitalization or Prolonged Hospitalization
- Overdoses, Misuses, Abuses, Off-Label Use, Occupational Exposure, or Medication Error
- Drug Interactions
- Quality Defects and Falsified Medicinal Products

10.1.3 Reporting Requirements from Physician to Roche

10.1.3.1 Immediate Reporting Requirements from Physician to Roche

Certain events require immediate reporting to allow Roche and the regulatory authorities to take appropriate measures to address potential new risks associated with the use of the medicine. The physician must report such events to Roche immediately; under no circumstances should reporting take place more than 24 hours after the physician learns of the event. The following is a list of events that the physician must report to Roche within 24 hours after learning of the event, regardless of relationship to study medicine:

- SAEs
- Pregnancies

The physician must report new significant follow-up information for these events to Roche immediately (i.e., no more than 24 hours after becoming aware of the information). New significant information includes the following:

- New signs or symptoms or a change in the diagnosis
- Significant new diagnostic test results
- Change in causality based on new information
- Change in the event's outcome, including recovery
- Additional narrative information on the clinical course of the event

For reports of SAEs and non-serious AEs of special interest, including follow-up, physicians should record all case details that can be gathered immediately (i.e., within 24 hours) in the AE page of the eCRF and submit the report via the EDC system. A report will be generated and sent to Roche Drug Safety by the EDC system.

In the event that the EDC system is temporarily unavailable, please refer to Section 10.1.3.3.

Physicians must also comply with local requirements for reporting SAEs to the local health authority and EC.

10.1.3.2 Reporting Requirements for Non-Serious Adverse Events

For all non-serious AEs, including follow-up reports, physicians must record all case details that can be gathered within 30 calendar days of learning of the event on the AE section of the eCRF and submit the report via the EDC system. A report will be generated and sent to Roche Drug Safety or the relevant marketing authorization holder (for non-Roche studied products) no more than 24 hours after learning of the to allow appropriate reporting to relevant competent authorities.

In the event that the EDC system is temporarily unavailable, please refer to Section 10.1.3.3.

10.1.3.3 If EDC System is Temporarily Unavailable or not Used

In the event that the EDC system is temporarily unavailable, a completed paper reporting form should be faxed to the CRO immediately (i.e., no more than 24 hours after learning of the event) or within 30 days for non-serious AEs if not AEs of special interest, using the fax number provided to physicians.

Once the system is available again, all information should additionally be entered and submitted via the EDC system.

10.1.3.4 Reporting Requirements for Pregnancies

Pregnancies/Breastfeeding in Female Patients

Female patients of childbearing potential will be instructed to immediately inform the physician if they become pregnant during the study or within six months after the last dose of medicine. A Pregnancy Report should be completed by the physician immediately (i.e., no more than 24 hours after learning of the pregnancy) and sent to the CRO. Pregnancy should also be recorded as an AE on the eCRF. In addition, all pregnancies and their outcome should be reported in the Ocrelizumab Pregnancy Registry (Study WA40063), which is being conducted [in Germany and the US]. Pregnant women who have received ocrelizumab within 6 months prior to their last menstrual period or at any time during pregnancy (regardless of participation in any studies) will be offered participation in the pregnancy registry. The physician should

discontinue ocrelizumab and counsel the patient, discussing the risks of the pregnancy and the possible effects on the fetus. Monitoring of the patient should continue until conclusion of the pregnancy. Any SAEs associated with the pregnancy (e.g., an event in the fetus, an event in the mother during or after the pregnancy, or a congenital anomaly/birth defect in the child) should also be reported on the AE section of the eCRF.

Suspected adverse reactions that occur in infants following exposure to a medicinal product from breast milk should be reported to Roche Drug Safety.

Abortions

Any abortion should be classified as an SAE (as Roche considers abortions to be medically significant), recorded in the AE section of the eCRF, and reported to Roche immediately (i.e., no more than 24 hours after learning of the event; see Section 10.1.3.1).

Congenital Anomalies/Birth Defects

Any congenital anomaly/birth defect in a child born to a female patient exposed to the medicine, should be classified as an SAE, recorded in the AE section of the eCRF, and reported to Roche immediately (i.e., no more than 24 hours after learning of the event; see Section 10.1.3.1).

10.1.3.5 Reporting Requirements for Adverse Events originating from Patient Reported Outcomes

As health-related quality of life is a secondary endpoint of this study all AEs reported within the patient-reported outcome using the Treatment Satisfaction Questionnaire for Medication (TSQM1.4), Multiple Sclerosis Impact Scale (MSIS-29 v2), Clinical Global Impression (CGI), and Symbol Digit Modality Test (SDMT) should not be documented per default within the eCRF. During site review of the PRO questionnaire data the physician/study personnel should screen for additional potential safety information out of scope of the questionnaires. If the criteria for an adverse event have been met this must be reported using the Adverse Event eCRF, if not already documented.

As the Pharmacoeconomic outcome 'Work Productivity and Activity Impairment Questionnaire: Multiple Sclerosis (WPAI:MS)' is an exploratory endpoint of this study all AEs reported within the scope of the questionnaire should not be documented per default within the eCRF, but only if not MS-related AEs have been added by the patient.

10.1.4 Follow-Up of Patients after Adverse Events

10.1.4.1 Physician Follow-Up

The physician should follow each AE until the event has resolved to baseline grade or better, the event is assessed as stable by the physician, the patient is lost to follow-up, or the patient withdraws consent. Every effort should be made to follow all SAEs considered to be related to studied medicinal product until a final outcome can be reported.

During the study period, resolution of AEs (with dates) should be documented in the AE section of the eCRF and in the patient's medical record to facilitate SDV.

All pregnancies reported during the study should be followed until pregnancy outcome.

10.1.4.2 Roche Follow-Up

For all AEs, Roche or a designee may follow up by telephone, fax, electronic mail, and/or a monitoring visit to obtain additional case details and outcome information (e.g., from hospital discharge summaries, consultant reports, autopsy reports) in order to perform an independent medical assessment of the reported case.

10.2 SAFETY REPORTING REQUIREMENTS FOR NON-STUDIED MEDICINAL PRODUCTS

Although adverse event information is not being actively solicited for non-studied medicinal products, the physician/consumers are reminded to report any adverse reactions (for which they suspect a causal role of a medicinal product) that come to their attention to the marketing authorization holder of the suspected medicinal product, or to the concerned competent authorities via the national spontaneous reporting system.

In addition, the following should also be reported if occurring during exposure to a marketed medicinal product, even in the absence of adverse events (Special Situation Events):

- Pregnancy
- Breastfeeding
- Abnormal laboratory findings
- · Overdose, abuse, misuse, off-label use, medication error or occupational exposure
- Reports of lack of efficacy
- Product quality defects and falsified medicinal products
- Data related to a suspected transmission of an infectious agent via a medicinal product
- Drug interactions (including drug/drug, drug/food, drug/device and drug/alcohol)

When a patient is not exposed to a marketed medicinal product, but the physician/consumer becomes aware of the potential for a medication error, or an intercepted medication error, this should also be reported.

11. PUBLICATION OF DATA AND PROTECTION OF TRADE SECRETS

Regardless of the outcome of a study, Roche is dedicated to openly providing information on the study to healthcare professionals and to the public, both at scientific

congresses and in peer-reviewed journals. Roche will comply with all requirements for publication of study results.

The results of this study may be published or presented at scientific meetings. If this is foreseen, the physician must agree to submit all manuscripts or abstracts to Roche prior to submission for publication or presentation. This allows Roche to protect proprietary information and to provide comments based on information from other studies that may not yet be available to the physician.

In accordance with standard editorial and ethical practice, Roche will generally support publication of multicenter studies only in their entirety and not as individual center data. In this case, a coordinating physician will be designated by mutual agreement.

Appendix 1 List of Stand-Alone Documents Not Included in the Protocol

List of contact details of responsible parties

Appendix 2 Data Collection Overview (as per Standard of Care)

Please see Table 1 in section 8.4.2.

Appendix 3 Methods for Assessing and Recording Adverse Events

- 3.1 Assessment of Severity of Adverse Events
- 3.2 Assessment of Causality of Adverse Events
- 3.3 Procedures for recording Adverse Events

Appendix 3.1 Assessment of Severity of Adverse Events

The AE severity grading scale for the NCI CTCAE (v4.0) will be used for assessing AE severity. The table below will be used for assessing severity for AEs that are not specifically listed in the NCI CTCAE.

Adverse Event Severity Grading Scale

Grade	Severity
1	Mild; asymptomatic or mild symptoms; clinical or diagnostic observations only; or intervention not indicated
2	Moderate; minimal, local, or non-invasive intervention indicated; or limiting age-appropriate instrumental activities of daily living ^a
3	Severe or medically significant, but not immediately life-threatening; hospitalization or prolongation of hospitalization indicated; disabling; or limiting self-care activities of daily living b, c
4	Life-threatening consequences or urgent intervention indicated d
5	Death related to AE d

Note: Based on the NCI CTCAE (v4.0), which can be found at: http://ctep.cancer.gov/protocolDevelopment/electronic_applications/ctc.htm

^a Instrumental activities of daily living refer to preparing meals, shopping for groceries or clothes, using the telephone, managing money, etc.

^b Examples of self-care activities of daily living include bathing, dressing and undressing, feeding oneself, using the toilet, and taking medications, as performed by patients who are not bedridden.

^c If an event is assessed as a "significant medical event," it must be reported as an SAE (see Section 10.1.3.1 for reporting instructions), per the definition of SAE in Section 10.1.1.2.1.

Grade 4 and 5 events must be reported as SAEs (see Section 10.1.3.1 for reporting instructions), per the definition of SAE in Section 10.1.1.2.1.

Appendix 3.2 Assessment of Causality of Adverse Events

Physicians should use their knowledge of the patient, the circumstances surrounding the event, and an evaluation of any potential alternative causes to determine whether or not an AE is considered to be related to the study medicine, indicating "yes" or "no" accordingly. The following guidance should be taken into consideration:

- Temporal relationship of event onset to the initiation of study medicine
- Course of the event, considering especially the effects of dose reduction, discontinuation of study medicine, or reintroduction of study medicine (when applicable)
- Known association of the event with the study medicine or with similar treatments
- Known association of the event with the disease under study
- Presence of risk factors in the patient or use of concomitant medications known to increase the occurrence of the event
- · Presence of non-treatment-related factors that are known to be associated with the occurrence of the event

For patients receiving combination therapy, causality will be assessed individually for each of the medicinal product.

Appendix 3.3 Procedures for recording Adverse Events

Appendix 3.3.1 Infusion-Related Reactions

AEs that occur during or within 24 hours after studied medicinal product administration should be captured as individual signs and symptoms in the AE section of the eCRF rather than an overall diagnosis (e.g., record dyspnea and hypotension as separate events rather than a diagnosis of infusion-related reaction).

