Overall, ocrelizumab demonstrated a favorable safety profile in RMS and PPMS patients The proportion of patients with adverse events (AEs) was similar in ocrelizumab patients compared with interferon β -1a (both 83.3%) or placebo patients (95.1% [ocrelizumab] vs. 90.0% [placebo]). The most common AEs were infusion-related reactions, nasopharyngitis, and urinary tract infections. Patients treated with ocrelizumab (versus interferon β -1a or placebo) reported more herpes virus-associated infections than patients who received interferon β -1a or placebo (RMS trials: 5.9% vs. 3.4%; PPMS trial: 4.7% vs. 3.3%), infusion-related reactions (RMS trials: 34.3% vs. 9.7%; PPMS trial: 39.9% vs. 25.5%), and upper respiratory tract infections (RMS trials: 15.2% vs. 10.5%; PPMS trial: 10.9% vs. 5.9%). The overall percentage of patients reporting a serious infection was lower in ocrelizumab-treated patients RMS trials compared to interferon β -1a-treated patients (1.3% vs. 2.9%), and similar in PPMS trials (6.2% [ocrelizumab] and 5.9% [placebo]).

In the pivotal ocrelizumab trials eight deaths occurred (RMS trials: 2 interferon β -1a patients [suicide and mechanical ileus] and 1 ocrelizumab patient [suicide]; PPMS trial: 1 placebo patient [road traffic accident] and 4 ocrelizumab patients [pulmonary embolism, pneumonia, pancreatic carcinoma, and pneumonia aspiration]) (Hauser et al. 2017; Montalban et al. 2017). The proportion of patients experiencing a serious adverse event (SAEs) was similar between ocrelizumab and the comparator groups (RMS trials: 6.9% [ocrelizumab] and 8.7% [interferon β -1a]; PPMS trial: 20.4% [ocrelizumab] and 22.2% [placebo]), In controlled studies, the pooled overall incidence of a first neoplasm among patients with MS who were treated with ocrelizumab (Phase II study, OPERA I & II, and ORATORIO) was 0.40 per 100 patient-years of exposure (6467 patient-years of

exposure), as compared with 0.20 per 100 patient-years for pooled comparator groups (interferon β-1a or placebo, 2053 patient-years of exposure) (Montalban et al. 2017).

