8.3 VARIABLES

8.3.1 Primary Safety Outcome Measures

The primary outcome measure for this study is as follows:

 incidence and type of uncommon AEs (i.e. AEs with an incidence rate of at least 0.1% [1 out of 1000 patients] at least once) and death with primary and underlying causes in patients with MS newly exposed to ocrelizumab

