8.5 STUDY SIZE

The primary objective of this study is to investigate the occurrence of uncommon adverse events in multiple sclerosis patients receiving treatment with ocrelizumab over a maximum time period of 10 years. The sample size is thus planned to allow for the detection of adverse events with an incidence rate of at least 0.1% (1 out of 1000 patients) at least once with a probability of 95%. Applying the Poisson distribution model for uncommon events, this results in a total sample size of approximately 3000 patients. Taking into account that ocrelizumab is currently the only approved disease modifying medication for PPMS and the resulting unmet need in this population approximately 700-1000 are expected to be PPMS patients. Patient recruitment and observation will take place at approximately 250 centers.

With the sample size of 3000 patients in this non-interventional study (NIS), following precision of the estimation of incidence rates in terms of 95% confidence intervals (Clopper-Pearson) can be obtained:

Table 2 95% Confidence Intervals for the Primary Safety Outcome Measures Based on 3000 Patients Receiving Ocrelizumab

Number of AE events/observed AE incidence	95% Confidence Interval (Clopper-Pearson) for the incidence rate
3 (0.1%)	[0.02%; 0.29%]
15 (0.5%)	[0.28%; 0.82%]
30 (1.0%)	[0.68%; 1.42%]

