Characterization based on relevant baseline data (age, PPMS history, status at start of PPMS treatment) will be performed by means of descriptive statistics for continuous data or frequency tables for categorical data. Previous and concomitant diseases will be coded and presented according to the MedDRA terminology. Summary tables will be provided for the SS and the FAS.

Analysis of primary endpoint

The analysis of the primary endpoint will be done on the safety analysis population. Incidence rates of adverse events will be calculated on the basis of system organ class and preferred term of the Medical Dictionary for Regulatory Activities (MedDRA) and presented along with two-sided 95% confidence intervals (Clopper-Pearson). In addition time adjusted analyses will be done based on patient years.

The analysis of safety outcomes/variables is based on the incidence and severity (NCI CTCAE grading) of all AEs and SAEs reported.

Events rates per 100 patient years (of treatment exposure) will be determined along with corresponding 95% confidence intervals.

Other safety analyses

Other safety endpoints will be analyzed descriptively in a similar fashion.

Selected lab outcomes/variables will be presented graphically, e.g. boxplots of the median, interquartile range, extreme values and outliers over time or mean and additional corresponding confidence intervals over time, based on standard units (SI units).

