Appendix 3.3.2 Diagnosis versus Signs and Symptoms

For AEs, other than infusion-related reactions (see Section 3.3.1) a diagnosis (if known) should be recorded in the AE section of the eCRF rather than individual signs and symptoms (e.g., record only liver failure or hepatitis rather than jaundice, asterixis, and elevated transaminases). However, if a constellation of signs and/or symptoms cannot be medically characterized as a single diagnosis or syndrome at the time of reporting, each individual event should be recorded in the AE section of the eCRF. If a diagnosis is subsequently established, all previously reported AEs based on signs and symptoms should be nullified and replaced by one AE report based on the single diagnosis, with a starting date that corresponds to the starting date of the first symptom of the eventual diagnosis.

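### Appendix 3.3.1 has infusion reactions entered only as separate symptoms, names no means of regrouping them, and as worded also covers events that are not reactions

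*Protocol*

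**What the plan says.** Appendix 3.3.1 of the protocol is headed for infusion-related reactions, but its sentence is about "AEs that occur during or within 24 hours after studied medicinal product administration". These "should be captured as individual signs and symptoms in the AE section of the eCRF rather than an overall diagnosis". Its example is to enter dyspnea and hypotension as two events and not as one reaction. The verb is should, but no exception is given.

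Appendix 3.3.2 sets the opposite rule for everything else: "For AEs, other than infusion-related reactions (see Section 3.3.1) a diagnosis (if known) should be recorded in the AE section of the eCRF". It also has earlier symptom entries withdrawn and replaced once a diagnosis is known. Because infusion-related reactions are exempted at the start of that paragraph, this later repair does not apply to them.

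For the primary endpoint, Section 8.7.1 states: "Incidence rates of adverse events will be calculated on the basis of system organ class and preferred term". Section 8.3.1 defines the uncommon events as "AEs with an incidence rate of at least 0.1% [1 out of 1000 patients] at least once", which is a floor without a ceiling. Section 8.3.2 lists the incidence of all adverse events and of serious infections among the secondary safety endpoints.

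Section 6.2 reports from the pivotal trials: "The most common AEs were infusion-related reactions, nasopharyngitis, and urinary tract infections". It gives infusion-related reactions in 34.3% (RMS) and 39.9% (PPMS) of patients on ocrelizumab, counted as one concept.

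**The concern.** The recording rule and the counting rule do not fit together. One reaction with two symptoms becomes two preferred terms, and each is added to the same term arising from any other cause. The term for the reaction itself stays near zero by construction, although the protocol names it first among the most common events. Section 8.1.2 says the study should show the incidence of expected events as well as uncommon ones, and the stated tables would not do so for this one.

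The second problem is scope. Read literally, the rule covers any event in the 24-hour window, so a site could split a true diagnosis with onset in that window into its symptoms. If that diagnosis is an infection, a secondary endpoint is affected. Both problems arise at data entry, and a judgement that sites were told not to enter is hard to recover years later.

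**Working it through.** **1. The plan's own figures.** Section 8.5 plans for "detection of adverse events with an incidence rate of at least 0.1% (1 out of 1000 patients) at least once with a probability of 95" percent. Under the Poisson model, N = −ln(0.05)/0.001 = 2995.7, so about 3000. With N = 3000, the chance of at least one case is 1 − exp(−3000 × 0.001) = 1 − exp(−3) = 95.02%. The Clopper-Pearson intervals in Table 2 also reproduce: 3 events give 0.02% to 0.29%, 15 give 0.28% to 0.82%, and 30 give 0.68% to 1.42%. None of this depends on how reactions are recorded, so the point does not touch the sample size.

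**2. Size of the concept that is not counted.** Inputs are the MS-type split in Section 8.1 (2000–2300 RMS, 700–1000 PPMS) and the rates in Section 6.2. Assumptions: trial rates carry over to routine care, and every reaction is captured.

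- 2300 × 0.343 + 700 × 0.399 = 788.9 + 279.3 = 1068.2 patients, or 1068.2/3000 = 35.6% (95% CI 33.9% to 37.3%).
- 2000 × 0.343 + 1000 × 0.399 = 686 + 399 = 1085 patients, or 1085/3000 = 36.2% (95% CI 34.4% to 37.9%).

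If reactions occurred in only 10% to 20% of patients (an assumption), the count would be 300 to 600.

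**3. Why the preferred-term table cannot rebuild it.** If two symptom terms are seen in n₁ and n₂ patients, the number with at least one of them lies between max(n₁, n₂) and n₁ + n₂. For example, two rows of 534 patients each are compatible with anything from 534 to 1068 affected patients. Patient-level data resolve this overlap. They do not show which of those symptoms belonged to a reaction, because the same term also arises from other causes.

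**4. How far a derived composite goes.** Section 8.4.2 and Table 1 name administration dates, dose and frequency, but no clock time. Suppose the infusion ends at hour t of its calendar day. Counting that day alone covers the next 24 − t hours, which is 24 or fewer. Counting that day and the next covers 48 − t hours, which is 24 or more. Dates alone therefore give a window that is too short or too long. The causality item in Appendix 3.2 asks whether the event is related to the medicine, yes or no. Adding it removes many coincident events, but relatedness is not a judgement that the event was an infusion reaction.

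**5. Scope, with the two rules side by side.** Take an infection whose onset falls within 24 hours of an infusion. The sentence in Appendix 3.3.1 asks for symptoms and no diagnosis. Appendix 3.3.2 asks for the diagnosis, since the event is not an infusion-related reaction. Both instructions apply and they are opposite. A site that follows the first enters symptoms, and the event may then be missed when infections are counted by coded term.

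**The case against.** The case on the other side is substantial. Symptom-level recording is deliberate, is stated consistently in both appendices, and keeps detail that suits the aim of characterizing events. Defining a composite is ordinary SAP content under Section 8.7, and the SAP is not at hand. The eCRF is not shown either and may already hold a marker. No objective promises an infusion-reaction rate as such. The heading of Appendix 3.3.1 and the cross-reference in Appendix 3.3.2 suggest that the rule was meant for reactions only.

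Much of this stands, and it rules out three stronger conclusions that a reader might draw.

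- That the study can report no incidence at all. An approximate composite from dates, onset and causality remains possible.
- That reaction symptoms contaminate a low-frequency band of the primary list, such as 0.1% to 1.0%. Section 8.3.1 sets only a floor, so a reaction diagnosis would be on the same list, and the documents give no symptom mix from which to count terms. Dyspnea after an infusion is also a genuine event. The harm is splitting and mixing of causes.
- That a flag would make the result directly comparable with 34.3% and 39.9%. Section 8.2.2 allows enrolment up to 30 days after treatment start, and Section 10.1.2.1 collects events only from enrolment. The two initial infusions are two weeks apart, so reactions to both may precede collection.

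The objection does not remove the data-capture problem. A SAP can group what was entered, but it cannot supply a reaction judgement that the form did not ask for. The likely intent of Appendix 3.3.1 does not settle what its sentence tells sites to do.

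**Conclusion.** The point holds in a limited form. The protocol directs that the reaction diagnosis not be entered, names no flag or link to replace it, and bases its incidence analysis on preferred terms. That analysis therefore yields no infusion-related reaction incidence and mixes reaction symptoms with the same terms from other causes; a derived composite would be approximate. Separately, the literal scope of Appendix 3.3.1 contradicts Appendix 3.3.2 for other events within 24 hours, and the two must be reconciled.

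The 1,068 to 1,085 patients indicate scale only and rest on trial rates and full capture. How many infections would be split cannot be estimated from the documents. The conclusion about flags rests on what the protocol specifies, since the eCRF is not available. The change is worth making early, but it is not a flaw in the sample size or in the primary definition.

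**What to change.** - Limit Appendix 3.3.1 to events that the physician judges to be infusion-related reactions, and state that all other events within 24 hours follow Appendix 3.3.2.
- Unless the eCRF already has one, add to the adverse event page an infusion-related reaction yes/no field with a link number that ties together the symptoms of one reaction.
- Report the reaction as one concept next to the symptom-level preferred-term table, and note that reactions before enrolment may be missing.

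The cost is a little extra entry at infusion visits, one form field and one extra table. The symptom detail is kept and the sample size stays as it is.
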